Emollient check ^g		X	X	X	X	X	X	X	X	X		

- ^a Participants who withdraw from the study early will have an Early Termination Visit and complete the assessments specified for Early Termination Visit. If due to treatment failure, this visit should be arranged within 72 hours of the start of any AD therapy, when possible. The participant will also be asked to have a final telephone call 28 days (+3 days) after taking their last dose of IMP for safety assessments. The date of this telephone call will be considered the end of study date for these participants.
- ^b Rescue Therapy Unscheduled Visit to be scheduled when rescue therapy is given outside of a scheduled visit. This visit shall be repeated each time a course of rescue therapy is considered/requested.
- ^c Informed consent (and re-consent, as applicable) must be obtained by the Principal Investigator or a licensed physician investigator (i.e., Sub-Investigator) per Good Clinical Practice (GCP) and local guidelines.
- ^d Inclusion/exclusion criteria to be assessed before first dose of IMP. Screening laboratory results will be used to confirm eligibility at Day 1 Visit.
- ^e Smoking status to include whether current-smoker, ex-smoker or never smoker, and to quantify current usage and total pack-year history.
- ^f A physical examination (PE) will be conducted at every visit. At Screening, Day 1 and Week 16 a full PE will be performed, and the following body systems will be evaluated: general appearance, cardiovascular, respiratory, gastrointestinal, musculoskeletal, central nervous system, lymph nodes and skin. At Weeks 2, 4, 8 12 and 20, a brief PE will be performed, and the following body systems will be evaluated: general appearance, cardiovascular, respiratory, gastrointestinal and skin.
- ^g BMI will be calculated from the height (collected at Screening) and weight.
- ^h Women of child-bearing potential only. Serum HCG at Screening. Pregnancy testing (urine) will be performed at the visits indicated and if a menstrual cycle is missed or if pregnancy is otherwise suspected.

- i A single ECG tracing is to be obtained on the day of the visit approximately 5 minutes after the participant has rested. If, in the opinion of the Investigator, there appear to be clinically significant findings, repeat tracings should be obtained, as necessary.
- j Blood pressure, heart rate, respiratory rate, and temperature will be measured after approximately 5 minutes after the participant has rested.

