11.4.4. Analysis of Secondary Estimands

Continuous secondary estimands will be analyzed using a mixed model for repeated measures (MMRM) with parameters for treatment group, visit, baseline IGA score and relevant baseline score and the interaction for treatment*visit.

For the potential covariates of body mass index, gender, race and region: those covariates found to be significant in the primary analysis will be included in all models regardless of significance in order to ensure comparability of the models.

Least squares mean estimates and their 95% confidence intervals (CI) will be presented for the endpoint value at each visit. Treatment differences between each EDP1815 group and the pooled placebo group will be estimated using LS mean differences, 95% CI and p-values. Pairwise treatment differences between EDP1815 groups will be estimated with LS mean differences and 95% CI.

Least square mean (95% CI) estimates will be plotted against visit. Least square mean (95% CI) treatment differences between each EDP1815 treatment group and the pooled placebo group will also be plotted against visit.

Response estimands will be analyzed with a generalized linear mixed effects model with a logit link function. Treatment, visit, baseline IGA and the appropriate baseline questionnaire score will be included as parameters together with the treatment*visit interaction. Odds ratios with 95% CIs and p-values for each EDP1815 group compared to the relevant pooled placebo group at each visit will be presented. Odds ratios and 95% CIs will be presented for any comparisons between two EDP1815 treatment groups.

In the event that there are no responders in one of the treatment groups at a visit, data from that visit will be excluded from the model and only summary statistics will be produced showing the number and percentage of responders at that visit.

Count estimands will be analyzed with a Poisson regression model fitted with treatment and baseline IGA as covariates. An offset of log (days in study) will also be included in the model to account for any data from participants who withdrew early from the study. If the distribution of the count data suggests over-dispersion and/or zero inflation, then other models including the negative binomial or zero-inflated Poisson model may be considered.

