7.1.1.2 Full Analysis Population

The full analysis population will consist of all participants who were randomised to treatment.

All analyses using the full analysis population will group participants according to randomised treatment.

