- Cohort 3 Placebo
- Cohort 3 EDP1815
- Cohort 4 Placebo (final analysis only)
- Cohort 4 EDP1815 (final analysis only)
- All Placebo
- All EDP1815
- Total

For cohorts 1-3 efficacy outputs, columns will be ordered and labelled as follows:

- All Placebo
- Cohort 1 EDP1815
- Cohort 2 EDP1815
- Cohort 3 EDP1815
- Cohorts 2+3 EDP1815
- All EDP1815

For cohort 4 efficacy outputs, columns will be ordered and labelled as follows:

- Cohort 4 Placebo
- Cohort 4 Matched Placebo
- Cohort 4 EDP1815
- Cohort 1 EDP1815

For concomitant medication and safety outputs, columns will be ordered and labelled as follows:

- All Placebo
- Cohort 1 EDP1815
- Cohort 2 EDP1815
- Cohort 3 EDP1815
- Cohort 4 EDP1815 (final analysis only)
- All EDP1815

For the analysis:

- For study disposition summaries where it is appropriate to report information on participants who failed screening, the enrolled population will be used.
- For safety summaries, where data is assigned to specific scheduled visits, the safety population with SDPS1 will be used.
- For safety summaries, where all other safety data is presented (including adverse events and worst-case change from baseline endpoints), the safety population with SDPS2 will be used.
- For the primary estimand and all secondary and exploratory estimands, full analysis population with EDPS1 will be used.
- For the supplementary estimands for the primary endpoint, full analysis population with EDPS2-EDPS5 will be used.
- Selected secondary response endpoints will also have secondary supplementary estimands: full analysis population with EDPS2 and EDPS6 will be used for endpoints based on EASI, vIGA and PP-NRS.
- For the secondary count endpoints, full analysis population with EDPS7 will be used.
- For the exploratory endpoints, full analysis population with EDPS1 will be used.
- For all other summaries and analyses the full analysis population will be used.

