9.4.3.1 Estimands

The population summary measure of interest will be the rate ratio between treatment groups specified in [Section 9.4](#).

Additionally, participants with rescue therapy courses recorded in CRF but with duration of more than 8 days (adjusted for dose frequency) will be excluded from the analysis due to the potentially incorrect rescue therapy data record.

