9.4.3.2 Main Analytical Approach

A Poisson regression model fitted with treatment and baseline vIGA as covariates. An offset of $\log(\text{days in study})$ will also be included in the model to account for any data from participants who withdrew early from the study. For participants who withdrew treatment early days in study will be calculated up to the end of treatment date or the end of period whichever occurs first. For

participants who completed treatment up to Week 16 days in study will be calculated up to the end of period.

In case of a greater variability among counts than expected for Poisson distribution, other models may be used (including negative binomial and zero inflated Poisson (ZIP)).

Number of courses of TCS/TCI rescue therapy endpoint will be evaluated for the following periods: Weeks 1-4, 5-8, 9-12, 13-16 and for Weeks 1-16.

Number of days requiring TCS/TCI rescue therapy endpoint will be evaluated for the following periods: Weeks 1-8, 9-16 and Weeks 1-16.

The model will be run separately for each period. Only participants with at least one visit performed in a period will be included in this period model. An offset of $\log(\text{days in the period})$ will also be included in the model based on the number of days from the first visit in the period to the last visit in the period.

Model predicted event rates and their 95% CIs will be presented for each treatment group. Rate ratios with 95% CIs and p-values for each EDP1815 group (including cohorts 2+3 EDP1815 and all EDP1815 groups) compared to the relevant pooled placebo group at each visit will be presented. Rate ratios and 95% CIs will be presented for any comparisons between two EDP1815 treatment groups. If ZIP model will be used, odds ratios for no rescue medication used and the 95% CIs will also be presented.

Number of courses of TCS/TCI rescue therapy in each period will be also plotted as histogram.

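### Rescue-count models: two exposure offsets, one of which is not time at risk; evaluation periods reversed between sections; and whole participants deleted on the outcome record

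*SAP*

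**What the plan says.** **Offset.** Protocol 11.4.4 has a single offset: "An offset of log (days in study) will also be included in the model to account for any data from participants who withdrew early". SAP 9.4.3.2 repeats it and adds that, for those who stop treatment early, "days in study will be calculated up to the end of treatment date or the end of period whichever occurs first". The same section then says each period has its own model, that "Only participants with at least one visit performed in a period will be included in this period model", and that an offset for days in the period is also included, "based on the number of days from the first visit in the period to the last visit in the period". It does not say whether the second replaces the first, or to which period a boundary visit such as Week 4 or Week 8 belongs.

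**Periods.** Protocol Table 11-2 (footnotes 5 and 6) and SAP 4.2 evaluate courses in Weeks 1-8 and 9-16, and days in the four 4-week periods. SAP 5.3.3.14 and 9.4.3.2 evaluate courses in the four 4-week periods, and days in Weeks 1-8 and 9-16. All four places also include Weeks 1-16.

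**Who is analysed.** SAP Section 8: "For the secondary count endpoints, full analysis population with EDPS7 will be used". SAP 7.1.1.2: "The full analysis population will consist of all participants who were randomised to treatment". SAP 7.1.2.7 and 9.4 and protocol 11.3.2 describe EDPS7 as holding everything collected up to completion or withdrawal. Yet SAP 9.4.3.1 states that "participants with rescue therapy courses recorded in CRF but with duration of more than 8 days (adjusted for dose frequency) will be excluded" because the record may be wrong. Separately, SAP 5.3.3.14 classes a TCS/TCI course as rescue only if it lasts no more than 8 days.

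SAP Section 13 lists other changes to the rescue endpoints, but not the second offset, the period swap or the exclusion.

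**The concern.** A Poisson offset should be the log of the time during which an event could have been counted. The gap between two clinic visits is something else: it depends on where visits fall and whether they were attended. SAP 5.3.3.14 counts rescue days up to the end of the period, so numerator and denominator can cover different stretches of time. Fitting both offsets together is no way out, since it would divide the count by the product of two exposures.

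The reversed periods leave it open which secondary analyses are the planned ones.

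The 8-day rule selects randomised participants on a post-randomisation record of the outcome being analysed. SAP 5.3.3.14 already keeps a long course out of the rescue definition. What 9.4.3.1 adds is the loss of the rest of that participant's data, including valid shorter courses. At stake are the displayed event rates, the rate ratios and their p-values for courses and days of rescue, and the same analyses for Cohort 4, which follow the main SAP.

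**Working it through.** The plan gives no figure to reproduce here, so the check applies its rules to its own visit schedule.

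**1. Visit-span offset.** Visit days from protocol Table 4-1: 1, 15, 29, 57, 85, 113. Visits carry their nominal label (SAP 7.7). Span = last minus first visit day in the period.

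| Weeks | Days at risk | Boundary visit counted once | Boundary visit shared |
|---|---|---|---|
| 1-4 | 28 | 29 − 1 = 28 | 29 − 1 = 28 |
| 5-8 | 28 | 57 − 57 = 0 | 57 − 29 = 28 |
| 9-12 | 28 | 85 − 85 = 0 | 85 − 57 = 28 |
| 13-16 | 28 | 113 − 113 = 0 | 113 − 85 = 28 |
| 1-8 | 56 | 57 − 1 = 56 | 57 − 1 = 56 |
| 9-16 | 56 | 113 − 85 = 28 | 113 − 57 = 56 |
| 1-16 | 112 | 113 − 1 = 112 | 113 − 1 = 112 |

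Counted once, three of the four 4-week periods hold a single visit. The one-visit rule admits those participants, and log(0) is undefined. Shared, the span is correct for anyone attending every visit. But a participant who misses only Week 8 gets 0 days in Weeks 5-8 and 9-12, and 29 − 1 = 28 and 113 − 85 = 28 days in Weeks 1-8 and 9-16, while at risk for 28, 28, 56 and 56.

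**2. Effect on a rate ratio (illustration; inputs assumed).** Weeks 9-16, shared boundaries, true ratio 0.60, everyone at risk for 56 days. A share m of each arm misses Week 16 and so has a span of 28 days. Estimated ratio = 0.60 × (1 − m_placebo/2) / (1 − m_active/2).

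- 10% in both arms: 0.60
- placebo 20%, active 10%: 0.60 × 0.90/0.95 = 0.568
- placebo 30%, active 10%: 0.60 × 0.85/0.95 = 0.537
- placebo 10%, active 30%: 0.60 × 0.95/0.85 = 0.671

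The ratio moves only when missed visits differ between arms, and it can move either way.

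**3. Deletion rule (illustration; inputs assumed).** Rescue users: u = 40% on placebo, 25% on active. Courses per user: 1.5, or 2.5 for the fraction f of users with a long course. Keeping all: u(1 − f)1.5 + uf × 2.5. Deleting: u(1 − f)1.5 / (1 − uf).

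- f = 20% in both arms: kept, (0.300 + 0.125)/(0.48 + 0.20) = 0.625; deleted, (0.300/0.95)/(0.48/0.92) = 0.605.
- f = 20% placebo, 10% active: kept, (0.3375 + 0.0625)/(0.48 + 0.20) = 0.588; deleted, (0.3375/0.975)/(0.48/0.92) = 0.663.

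The keeping-all figures count the long courses as events.

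**4. Imputed stop dates.** SAP 7.3.1 sets a stop date with a missing day to the last day of its month. A 7-day course from the 3rd to the 9th of a 31-day month then runs from the 3rd to the 31st: 31 − 3 + 1 = 29 days. For daily use, a true 7-day course stays at 8 days or fewer only if it really stopped on one of the last two days of a month: 2 × 12 = 24 of 365 start dates. For the other 341, imputation alone exceeds the limit. This is conditional on a missing stop day and is not an expected deletion rate.

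**The case against.** The strongest reply is that much of this is drafting. A log of zero stops the program rather than biasing a result unseen; sharing boundary visits gives exact exposure for full attenders; and an error common to everyone rescales the displayed rates but cancels from the rate ratio. All of that stands. What remains is that the SAP does not state the shared reading, and that even this reading fails when a visit is missed.

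A second reply is that 9.4.3.1 gives a data-quality reason and can be read as a specific exception to Section 8. The reason is fair, but it supports querying or excluding a doubtful record. It does not support removing a participant's sound records, nor describing what is left as everyone randomised.

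Third, keeping everyone is not enough. Under 5.3.3.14 a retained participant's long course would score as no rescue, which is also a distortion. This is correct, and the fix below allows for it.

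A reader might also infer that exposure depends on the outcome, since the protocol's schedule has a "Rescue Therapy Unscheduled Visit to be scheduled when rescue therapy is given outside of a scheduled visit". SAP 7.7 does not support that: data from those visits enter tables only for last off-rescue imputation, which EDPS7 does not use. Section 7.7 does not mention offsets by name, but it is the general convention. Because it also keeps visits at their nominal label, it equally does not support arguing that an early or late visit slips into the neighbouring period. Nor can a fixed inflation of the displayed rates be claimed, because 9.4.3.2 does not add a day to the span.

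**Conclusion.** The point holds on three counts: two incompatible offsets, one of which does not measure time at risk; periods stated in opposite ways with no declared change; and exclusion of randomised participants on a post-randomisation outcome record.

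The offset and deletion rules affect the two count endpoints, courses and days. The 8-day definition in 5.3.3.14 also affects the requirement-for-rescue endpoint, where someone whose only courses exceed 8 days counts as not requiring rescue. The Weeks 1-16 offset is largely unaffected for completers, and that period is common to all sections.

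It would be too much to say that the rate ratios are biased in a known direction. The documents give no rescue rates, no missed-visit rates by arm and no frequency of long or partly dated courses. The illustrations above show only that the ratio can move. The point does not reach EASI-50: in SAP Table 1, type 1 prohibited medication and permitted TCS/TCI are handled alike. No multiplicity-controlled claim depends on these endpoints (SAP 7.6), and their tables are not marked for top-level results. The correction should still be made, because p-values will be reported from models that, as written, are either undefined or depend on the analyst's choice.

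**What to change.** - **Offset:** delete the visit-span offset and the one-visit requirement. Use one offset: the log of calendar days at risk from period start to the earlier of period end or end of EDPS7 collection. EDPS7 ends at study discontinuation, whereas the first SAP offset stops at end of treatment.
- **Periods:** reconcile Protocol Table 11-2 and SAP 4.2, 5.3.3.14 and 9.4.3.2, and define the periods in study days. By default keep those of the protocol and SAP 4.2, since no change is declared.
- **Population:** keep all randomised participants in the main count analysis.
- **Course definition:** for the count and requirement-for-rescue endpoints, amend 5.3.3.14 so that sponsor-classified TCS/TCI rescue courses over 8 days count as rescue rather than as none. State how this fits with SAP 5.3.2.3, where TCS/TCI not considered rescue is type 1 prohibited medication. This is a counting rule only and says nothing about how long rescue may be given.
- **Data quality:** query long or date-imputed courses before lock. As sensitivity analyses, report the 8-day participant exclusion, and days truncated at 8 for courses whose dates remain imputed.
- **Record:** list the changes in SAP Section 13.

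The cost is SAP wording, simple reprogramming and a round of queries. The downside is that some long durations caused by recording or imputation may remain: the diary items in protocol 6.6.1 capture only confirmation of rescue use and may not settle every case.

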9.5 Exploratory Efficacy Analyses

All efficacy analysis details in this section are provided for cohorts 1-3 analysis.

For cohort 4 analysis the same approach will be used. Any differences and additional analyses will be described in the SAP Addendum.

9.5.1 Exploratory Efficacy Endpoints

The exploratory endpoints will be summarised using statistics appropriate to the endpoint as described below.

Continuous, time to event and response exploratory endpoints estimands will use the same intercurrent event strategy as the primary estimand (EDPS1 will be used). Where intercurrent event strategy is composite, for continuous endpoints value will be imputed with the last off-rescue observation.

Last off-rescue observation is defined as the last off-rescue observation in the period before the corresponding intercurrent event plus early termination visit in case of early study discontinuation (off-rescue is defined as data collected at least 28 days after use of rescue medication or type 1 prohibited medication).

Count exploratory endpoints and response subgroup endpoints will use EDPS7 (estimand includes all data as collected prior to completion or withdrawal from the study).

Exploratory estimands will be evaluated at all timepoints at which the relevant endpoints are collected.

9.5.1.1 Continuous Exploratory Endpoints

Continuous exploratory endpoints:

- Mean absolute change and percentage change from Screening in EASI Score.
- Changes from baseline in SF-12 MCS and PCS scores.
- Changes from baseline in HADS anxiety and depression scores.
- Changes from baseline in ADCT scores.
- Daily changes from baseline in the PP-NRS and SD-NRS (Timescale: Days 2 to 112).

The population summary measure of interest will be the mean value in each treatment group.

Endpoints other than PP-NRS and SD-NRS will be summarized as described in [Section 8](#).

Daily PP-NRS and SD-NRS endpoints will be listed and plotted.

9.5.1.2 Time to Event Exploratory Endpoints

Time to event exploratory endpoints:

- Time to first achievement of EASI-50.
- Time to first achievement of sustained EASI-50.
- Time to first achievement of EASI-75.
- Time to first achievement of vIGA of 0 or 1 with a 2-point improvement from baseline.
- Time to first achievement of vIGA of 0 or 1.
- Time to first achievement of a ≥ 2 point in improvement in PP-NRS score, in participants with a score of ≥ 2 at baseline.
- Time to first sustained ≥ 2 point in improvement in PP-NRS score, in participants with a score of ≥ 2 at baseline.
- Time to first achievement of a ≥ 4 point in improvement in PP-NRS score, in participants with a score of ≥ 4 at baseline.
- Time to first sustained ≥ 4 point in improvement in PP-NRS score, in participants with a score of ≥ 4 at baseline.
- Time to first achievement of a ≥ 2 point in improvement in SD-NRS score, in participants with a score of ≥ 2 at baseline.
- Time to first sustained ≥ 2 point in improvement in SD-NRS score, in participants with a score of ≥ 2 at baseline.

PP-NRS and SD-NRS time to event endpoints

The population summary measure of interest for the PP-NRS and SD-NRS endpoints will be the Kaplan-Meier estimates of proportion of responders at each week from 1 to 16 in each treatment group.

Censoring rules for these time to event endpoints are defined in [Section 5.3.3.10](#).

The total number of responders throughout the period and number of participants censored will be presented together with Kaplan-Meier estimates of proportion of responders at each week from 1 to 16 and the estimated median and quartiles for time to response.

A figure showing the estimated survival curves of each treatment group will also be presented.

Sustained PP-NRS and SD-NRS time to event endpoints

The population summary measure of interest for the PP-NRS and SD-NRS endpoints will be the Kaplan-Meier estimates of proportion of responders at each week from 1 to 14 in each treatment group.

Censoring rules for these time to event endpoints are defined in [Section 5.3.3.10](#).

The total number of responders throughout the period and number of participants censored will be presented together with Kaplan-Meier estimates of proportion of responders at each week from 1 to 14.

A figure showing the estimated survival curves of each treatment group will also be presented.

Other time to event endpoints

The population summary measure of interest for other endpoints will be the cumulative proportion to have achieved the event at each visit in each treatment group.

The number of participants meeting the criteria for the endpoint, and the number of participants 'at risk' of meeting the criteria at each visit will be presented together with the cumulative incidence and associated 95% CI. Cumulative incidence is calculated as the total number of events on or before the visit divided by the total number of participants at risk of the event.

For each endpoint, the cumulative incidences for each treatment group will be plotted against time as bars (with an 'error bar' for the corresponding 95% CI).

